8.10. Special Situation Reports

Special situation reports include reports of overdose, misuse, abuse, medication error, and reports of adverse reactions associated with product complaints.

- **Overdose:** Refers to the administration of a quantity of a medicinal product given per administration or cumulatively (accidentally or intentionally), which is above the maximum recommended dose according to the protocol. Clinical judgment should always be applied. In cases of a discrepancy in the drug accountability, overdose will be established only when it is clear that the patient has taken additional dose(s), or the Investigator has reason to suspect that the patient has taken additional dose(s).
- **Misuse:** Refers to situations where the medicinal product is intentionally and inappropriately used not in a way that is not in accordance with the protocol instructions or local prescribing information and may be accompanied by harmful physical and/or psychological effects.
- **Abuse:** Is defined as persistent or sporadic, intentional excessive use of a medicinal product, which is accompanied by harmful physical or psychological effects.
- **Medication error:** Is any unintentional error in the prescribing, dispensing, or administration of a medicinal product by a healthcare professional, patient, or consumer,

respectively. The administration or consumption of the unassigned treatment and administration of an expired product are always reportable as medication errors, cases of patients missing doses of investigational product are not considered reportable as medication error.

- **Product complaint:** Is defined as any written, electronic, or oral communication that alleges deficiencies related to the identity, quality, durability, reliability, safety, effectiveness, or performance of a drug or device after it is released for distribution. A Special Situations Report form will only be completed if a complaint is associated with an adverse drug reaction.

All special situation events as described above must be reported on the Special Situations Report form and faxed/emailed to [REDACTED] (contact information listed in Section 8.7) within 24 hours of knowledge of the event. All AEs associated with these special situation reports should be reported as AEs or SAEs as well as recorded on the AE eCRF and/or the SAE report form. Details of the symptoms and signs, clinical management, and outcome should be provided, when available.

8.11. Safety Endpoints

The safety endpoints include the following:

- Description of safety assessments by treatment group and dose. Safety assessments include AEs, SAEs, vital signs, ECG results, and clinical laboratory evaluations;
- Proportion of patients with AEs leading to discontinuation;
- Description and frequency of AESIs by treatment group; and
- Description of ADAs (binding and neutralizing).

8.12. Clinical Laboratory Evaluations

Samples for chemistry, hematology, urinalysis, and lipid laboratory evaluations will be obtained as indicated in Appendix A and assessed at the central laboratory. See Appendix B for a complete list of analytes. Lipids and subfractions will be assessed after 8 hours of fasting.

Serum pregnancy tests will be performed for women of childbearing potential only at Visits -1 and 11 and assessed at the central laboratory.

INR will be performed by the local laboratory only for patients currently receiving warfarin.

8.13. Vital Signs

Vital signs will be measured as indicated in Appendix A. Vital signs include temperature, respiratory rate, heart rate, and blood pressure. Patients may be re-evaluated within 2 weeks, at the discretion of the Investigator, if antihypertensive therapy has been started or increased as a result of initial blood pressure measured at Screening. Whenever possible, vital signs will be obtained after at least 5 minutes resting in the supine position or a semirecumbent position. Vital signs will be obtained prior to ECG recordings.

8.14. Electrocardiograms

ECGs will be performed as indicated in Appendix A. Standard 12-lead ECGs will be recorded in the supine position (or with the patient as flat as possible) after vital sign assessments. The ECG will be locally read by the Investigator.

8.15. Physical Examinations

Limited physical examinations will be performed as indicated in Appendix A. A limited physical examination will include examination of the skin, oropharynx, lungs, heart, abdomen, extremities (including feet), and any areas suggested by symptoms, with particular attention to signs of infection. This may be performed by a physician-Investigator. Abnormal findings will be recorded in the source documents.

9. STATISTICS

Details of all planned analyses will be provided in the Statistical Analysis Plan.

9.1. Analysis Populations

The following analysis populations are defined for the different types of data analysis:

- Intent-to-Treat (ITT) Population: all randomized patients;
- Per-Protocol Population: all randomized patients who complete the study and do not incur a significant protocol violation;
- PK Population: all randomized patients who receive study drug and have at least 1 postdose PK blood sample; and
- Safety Population: all randomized patients who receive study drug.

9.2. Statistical Methods

All study-collected data will be summarized by treatment group for the appropriate analysis population using descriptive statistics, graphs, and/or raw data listings. Descriptive statistics for continuous variables will include number of patients (n), mean, standard deviation (SD), median, first and third quartiles, minimum and maximum values for the observed value, and change from Baseline. Analysis of categorical variables will include frequency and percentage.

The Baseline value for hs-CRP level will be the average of all hs-CRP values prior to the administration of study drug. The Baseline value of other measures is defined as the last measurement collected prior to the administration of study drug, unless otherwise specified.

9.2.1. Analysis of Efficacy

For efficacy (PD) variables, the median difference between each active group and placebo will be analyzed. Efficacy analysis will be performed using the nonparametric Hodges-Lehmann method to estimate median differences between each active group and placebo, associated 95% confidence intervals, and p-values. Additionally, the nonparametric analysis will adjust for the randomization stratification variable CKD Stage (3 vs. 4 and 5)..

For the efficacy variables, the observed values and changes from Baseline will be summarized by treatment group using descriptive statistics and the ITT Population.

9.2.1.1. Primary efficacy (pharmacodynamic) analysis

The overall familywise error rate will be controlled at $\alpha = 0.05$ using the sequential testing procedure for the primary efficacy endpoint comparing the 2 dose levels of Ziltivekimab vs placebo. The high dose (30 mg) will be compared with placebo first. If the high dose is significant, then the low dose (15 mg) will be compared with placebo. The procedure will stop whenever a nonsignificant test occurs.

9.2.1.2. Sensitivity analysis

Sensitivity analysis will be performed for the primary efficacy endpoint using the following methods:

1. The nonparametric analysis method used to analyze the primary efficacy endpoint will be performed on the per-protocol population.
2. Analysis of hs-CRP on a log scale, using log of ratio to baseline as the outcome variable, will be performed using mixed models for repeated measures on the ITT population.
3. Sensitivity analysis will be performed on the ITT population using a pattern-mixture model using sequential modeling with multiple imputation on the log transformed hs-CRP data. Subjects in the active group who terminated early will be assumed to have no treatment effect. These subjects are assumed to copy the profile of placebo group and missing values are imputed based on the distribution estimated from the placebo group under the missing not at random assumption. The rest of missing values in the placebo arm and active arms will be imputed using the observed data under the missing at random assumption. The multiple imputation model will include factors such as treatment arm and CKD stage in addition to the data outcomes at each visit. Data will be log transformed prior to imputation, and imputed data will be back-transformed in the final imputed data. After the multiple imputation step, each log-transformed imputed dataset will be analyzed using the analysis of covariance model (not repeated measures and with no random effects) to produce treatment difference estimates for ratio to baseline, treatment ratio estimates, 95% confidence intervals, and p-values.

Details of sensitivity analysis will be provided in the statistical analysis plan (SAP).

9.2.2. Analysis of Pharmacokinetic and Pharmacokinetic-Pharmacodynamic Modeling

9.2.2.1. Pharmacokinetic data

A listing of PK blood sample collection times as well as derived sampling time deviations will be provided. A by-patient listing of all serum concentration-time data for each dose group will be presented. Ziltivekimab serum concentrations will be summarized by dose group and nominal time point using appropriate descriptive statistics (eg, n, arithmetic mean, SD, coefficient of variation [CV], minimum, median, maximum, geometric mean, and geometric CV).

For IL-6, results of PK parameters, such as AUC, will be summarized by dose group.

Individual and mean concentration-time profiles will be presented graphically.

9.2.2.2. Pharmacokinetic-pharmacodynamic modeling

PK-PD model parameters will be derived using plasma IL-6 levels to describe target engagement, with clinically meaningful PD parameters, such as hs-CRP. The specific model parameters to be estimated will be determined based on review of the observed data. The PD parameters to be included in the PD analysis will be determined following review of the study data.

A listing of PD blood sample collection times as well as derived sampling time deviations will be provided. A by-patient listing of all PD results and their corresponding change from Baseline value for each dose group will be presented. The observed and change from Baseline serum results will be summarized using descriptive statistics by dose group.

Graphical presentations, as appropriate for PD variables, may include the following: individual observed and percent change from Baseline serum concentration-time curves for each patient on

linear scale and arithmetic mean serum concentration-time curves by dose group on linear scale.

9.2.3. Analysis of Safety

9.2.3.1. Adverse events

The AE verbatim descriptions (Investigator terms from the eCRF) will be classified into medical terminology using the Medical Dictionary for Regulatory Activities (MedDRA). AEs will be coded to primary System Organ Class (SOC) and preferred term (PT) using the latest version of the MedDRA.

A TEAE is defined as an AE that initiated or worsened on or after the date of first dose of study drug up to the end of the Safety Follow-Up Period. For AEs occurring on the first dosing day, if the start time cannot be ascertained, the event will be counted as treatment emergent.

The number (percentage) of patients reporting TEAEs and SAEs for each PT will be tabulated by SOC, by SOC and severity, and by SOC and relationship to study drug. If more than 1 event occurs with the same PT for the same patient, the patient will be counted only once for that PT using the most severe or related occurrence for the summary by severity or relationship to study drug, respectively.

AESIs will be summarized by treatment group and dose.

9.2.3.2. Clinical laboratory evaluations

Clinical laboratory values (excluding efficacy laboratory parameters) will be summarized by treatment group, including changes from Baseline at each visit.

9.2.3.3. Vital signs

Vital signs and change from Baseline in vital signs will be summarized descriptively at each visit by treatment group. The number and percentage of patients with exceeding pre-defined absolute and relative threshold values (systolic blood pressure increase or decrease from Baseline >25% mmHg, >160 mmHg, or <90 mmHg; heart rate >100 beats per minute or <50 beats per minute; and respiration rate >24 breaths per minute) will be summarized.

9.2.3.4. Electrocardiograms

ECG interpretation (normal vs abnormal) will be summarized using frequency and percentage at each visit by treatment group. ECG intervals (ie, PR interval, QT interval, heart rate, and QTcF) will be summarized descriptively at each visit. The number and percentage of patients with exceeding pre-defined absolute and relative threshold values (PR interval >200 msec; QTcF >450 msec, >480 msec, and >500 msec; and QTcF increase from Baseline >30 msec and >60 msec) will be summarized.

9.2.3.5. Physical examination

Clinically significant new or worsening physical examination findings will be reported as AEs and will therefore be summarized as described for AEs.

9.2.3.6. Anti-drug antibodies

The immunogenic potential of Ziltivekimab will be assessed by summarizing the number and percentage of patients who develop detectable ADAs. ADA titers will be summarized descriptively for ADA positive samples, and the impact of ADA on PK will be assessed if data allows.

9.2.3.7. Bleeding events

Bleeding events will be classified using the TIMI Bleeding Classification in Table 3.¹⁴

Table 3 Thrombolysis in Myocardial Infarction Bleeding Classification

Parameter	Criteria
Major	Intracranial hemorrhage or a ≥ 5 g/dL decrease in the hemoglobin concentration or a $\geq 15\%$ absolute decrease in the hematocrit
Minor	Observed blood loss: ≥ 3 g/dL decrease in the hemoglobin concentration or $\geq 10\%$ decrease in the hematocrit. No observed blood loss: ≥ 4 g/dL decrease in the hemoglobin concentration or $\geq 12\%$ decrease in the hematocrit
Minimal	Any clinically overt sign of hemorrhage (including imaging) that is associated with a < 3 g/dL decrease in the hemoglobin concentration or $< 9\%$ decrease in the hematocrit

All TIMI definitions take into account blood transfusions, so that hemoglobin and hematocrit values are adjusted by 1 g/dL or 3%, respectively, for each unit of blood transfused. Therefore, the true change in hemoglobin or hematocrit if there has been an intervening transfusion between 2 blood measurements is calculated as follows: ΔHemoglobin = [baseline Hgb – post-transfusion Hgb] + [number of transfused units]; Δ Hematocrit = [baseline Hct – post-transfusion Hct] + [number of transfused units \times 3].
 
Hct = hematocrit; Hgb = hemoglobin; TIMI = Thrombolysis in Myocardial Infarction.
 
Source: Rao SV, O'Grady K, Pieper KS, et al. A comparison of the clinical impact of bleeding measured by two different classifications among patients with acute coronary syndromes. J Am Coll Cardiol. 2006;47(4):809-816
	

9.2.4. Interim Analysis

No interim analysis is planned for the study.

9.2.5. Sample Size Determination

The primary efficacy endpoint is the difference in the mean percent change in hs-CRP from Baseline to the End of Treatment (average of Week 10 and Week 12) between each active group and placebo. Based on the observed treatment difference of -60.74% between combined COR-001-01 active and placebo and the associated pooled SD of 16.893% in hs-CRP at Week 4 from the final analysis of study COR-001-SC1, a sample size of 6 patients per group provides 90% power with 2-sided $\alpha = 0.05$. Therefore, the planned sample size of 12 patients per group (total of 36 patients) will provide sufficient power for the study.

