5. STUDY TREATMENTS

5.1. Treatment Groups

Patients will be randomized in a 1:1:1 ratio to 1 of the following dose cohorts:

- Dose Cohort 1: Ziltivekimab 15 mg
- Dose Cohort 2: Ziltivekimab 30 mg
- Dose Cohort 3: Placebo

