3.4.1 Primary Efficacy Endpoints

Primary Analysis

The primary PD endpoint is the difference in the percent change in hs-CRP levels from Baseline (average of all hs-CRP values prior to the administration of study drug) to the End of Treatment (average of Week 10 and Week 12) between each active group and placebo.

The Hodges-Lehmann estimate for median of differences for each active group vs. placebo along with the 95% confidence intervals will be presented. P-value from the Wilcoxon test will also be presented. The nonparametric analysis will account for the covariate CKD Stage (3 vs. 4 and 5) by aligning responses within the strata defined by the covariate prior to analysis. Median and quartiles will also be presented for hs-CRP values at baseline, end of treatment, and percent change in hs-CRP from baseline to End of Treatment.

The sample SAS code for Hodges-Lehmann estimates for each treatment arm vs. Placebo can be found below:

.....

*Note: PCHG = Percent change in hs-CRP from baseline to End of Treatment (average of values at Week 10 and Week 12).

* CKD = CKD Stage (stage 3 vs. stage 4 and 5)

* TRT = Treatment group

* VISIT = Study Visit

*****;

```
proc npar1way data=efficacy (where=(TRT in (1, #) & VISIT = "End of Treatment")
    wilcoxon hl(refclass="1") alpha=.05 align=strata(hl);
    class TRT;
    strata CKD;
    var PCHG;
    ods output WilcoxonScores=WilcoxonScores HodgesLehmann=HodgesLehmann;
    output out=pvalue;
```

run;

The overall familywise error rate will be controlled at $\alpha = 0.05$ using the sequential testing procedure for the primary efficacy endpoint comparing the 2 dose levels of Ziltivekimab vs placebo. The high dose (30 mg) will be compared with placebo first. If the high dose is significant, then the low dose (15 mg) will be compared with placebo. The procedure will stop whenever a nonsignificant test occurs.

Sensitivity Analyses

Sensitivity analyses will be performed as follows:

- (1) The nonparametric analysis method used to analyze the primary efficacy endpoint will be performed on the PP population.

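### The stated 90% power at 6 patients per group does not follow from the plan's own inputs, which give 99.98%; the error is conservative, and the sentence needs correcting and its source study reconciling.

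*Protocol*

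**What the plan says.** Protocol 9.2.5 sizes the trial on means: "The primary efficacy endpoint is the difference in the mean percent change in hs-CRP from Baseline to the End of Treatment". The effect is an "observed treatment difference of -60.74% between combined COR-001-01 active and placebo", with an "associated pooled SD of 16.893% in hs-CRP at Week 4 from the final analysis of study COR-001-SC1". From these, at two-sided alpha 0.05, it states that "a sample size of 6 patients per group provides 90% power", and concludes that "the planned sample size of 12 patients per group (total of 36 patients) will provide sufficient power for the study". The synopsis and SAP 2.2.4 carry the same paragraph. None of the three names the test behind the power figure.

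Allocation is equal (Protocol 5.1: "Patients will be randomized in a 1:1:1 ratio to 1 of the following dose cohorts"), so each active-versus-placebo comparison is 1:1. The two doses are tested in fixed sequence, each at the full 0.05 (Protocol 9.2.1.1).

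The primary analysis is nonparametric. SAP 3.4.1 reports "The Hodges-Lehmann estimate for median of differences for each active group vs. placebo", with a p-value from a Wilcoxon test on responses aligned within CKD strata.

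Protocol 1.4.2 describes COR-001-SC1 as a single-dose subcutaneous study in moderate-to-severe CKD. Protocol 1.4.3 describes COR-001-01 as a multiple-dose intravenous study in hemodialysis patients.

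**The concern.** A difference of 60.74 against an SD of 16.893 is a standardised effect of about 3.6. With an effect that large, 6 per group should give power far above 90%, so the stated figure looks inconsistent with its own inputs. It is the only power figure in the plan, and the adequacy of 12 per group is drawn directly from it.

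Two further gaps stop a reader from repairing it. Without a named test, the calculation cannot be retraced. With two study labels in one sentence, the reader cannot tell which population, route and dosing pattern supplied the effect and the SD.

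What is at stake is whether the justification can be checked, and whether the margin behind 12 per group is known if the SD at Weeks 10 and 12 exceeds the Week 4 value used here.

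**Working it through.** **Inputs (Protocol 9.2.5):** difference 60.74; SD 16.893; two-sided alpha 0.05; stated result 90% at 6 per group; planned 12 per group.

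**Step 1. Standardised effect.** d = 60.74 / 16.893 = 3.596.

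**Step 2. Try to reproduce the stated figure by t-test.** The noncentrality is d × √(n/2), with 2n − 2 degrees of freedom. At n = 6 it is 3.596 × √3 = 6.23, on 10 df, with critical value 2.228. Power is **99.98%**, not 90%. At n = 12 it is 3.596 × √6 = 8.81, on 22 df, and power is above 99.99%.

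**Step 3. Size of the mismatch.** For 6 per group to give 90% by t-test, d would have to be 2.081. That means an SD of 60.74 / 2.081 = 29.2 with the difference as stated, or a difference of about 35.1 with the SD as stated.

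**Step 4. Other methods at 6 per group.**

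| Method | Power at 6 per group |
|---|---|
| Normal approximation, two-sided 0.05 | 99.999% |
| t-test, one-sided 0.05 | 99.998% |
| t-test, two-sided 0.025 | 99.91% |
| t-test, two-sided 0.01 | 99.4% |
| Three-group F test, 0.05 | 99.95% to 99.998% |
| Exact Wilcoxon, two-sided 0.05 (simulated) | about 99.9% |
| Noether's formula, two-sided 0.05 | 84.3% |
| Noether's formula, z = 1.645 (one-sided 0.05) | 90.7% |

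The Noether rows use power = Φ(√(6n) × (p − 0.5) − z), where p = Φ(3.596/√2) = 0.9945. At n = 6 the first term is 6 × 0.4945 = 2.967. Subtracting 1.960 gives 1.007 (84.3%); subtracting 1.645 gives 1.322 (90.7%). Only the last row is close to 90%, and it contradicts the two-sided alpha in the same sentence.

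**Step 5. The rank test at the planned size.** With normal data, equal SDs and no stratification, every one of 40,000 simulated trials with 12 per group was significant by exact Wilcoxon test on the stated inputs. Alignment by CKD stratum was not simulated, because the documents do not give the expected split between strata.

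**Step 6. Margin at 12 per group, difference held at 60.74.**

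| Power | Largest SD, exact Wilcoxon (simulated) | Largest SD, t-test |
|---|---|---|
| 90% | about 42 | about 44 |
| 80% | about 48 to 49 | about 51 |

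At the t-test limits (43.9 and 50.8 before rounding), Wilcoxon power is only about 87% and 76%. Quoting t-test limits would therefore overstate the margin of the planned analysis.

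**The case against.** The strongest objection is that the error harms nothing. On the stated inputs the design has more power than claimed, the conclusion that 12 per group suffices holds all the more, and no sample size, alpha or analysis would change. That stands, and it sets the severity. It does not make the stated figure right.

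A second objection is that the paragraph names no test, so a rank-based sizing cannot be ruled out; Noether's formula with a one-sided z gives 90.7% at 6 per group. This too stands in part: one cannot say that the sizing used a test foreign to the primary analysis. But that route needs a one-sided critical value, against the stated two-sided alpha, so it does not rescue the sentence.

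Three stronger readings are tempting, and the documents support none of them:

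- A reader might infer that 6 is a two-arm total misreported as a per-group number, because the t-test reaches 90.1% at 3 per group. Nothing in the documents says so. Nor is 3 per group a usable figure for a rank analysis: the smallest exact two-sided p-value with 3 against 3 is 2/20 = 0.10.
- A reader might infer that the difference comes from one study and the SD from another. The wording permits this. But COR-001 is also the drug's code (Protocol 1.1), so the label may be a slip for COR-001 active arms within COR-001-SC1. Only the double citation is established.
- A reader might infer that the trial is underpowered. That would need an SD well above 16.893, and the documents give no such value.

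**Conclusion.** The statement is wrong as written in all three places. The stated inputs give 99.98% power at 6 per group by t-test and about 99.9% by exact Wilcoxon test, against the stated 90%. The documents do not show whether the power, the sample size or an input is at fault. The sentence also cites two studies that the protocol describes separately, and they must be reconciled.

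The error is conservative. Taking the stated difference and SD at face value, 12 per group has over 99.9% power. This is a minor wording correction, with no consequence for the design unless the inputs themselves turn out to be wrong.

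The figures assume normal data with a common SD, 1:1 comparisons and no dropout; the sample-size section gives no dropout rate. The Wilcoxon figures are for the unstratified exact test and stand in for the aligned test.

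**What to change.** Keep 12 per group. In Protocol 9.2.5, the synopsis and SAP 2.2.4, make the same changes:

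1. State which study, and which arms of it, supplied the difference of -60.74 and the SD of 16.893.
2. Remove the 6-per-group power statement. Give instead the power of the planned 12 per group, computed for the planned CKD-aligned Wilcoxon test at two-sided 0.05, and name that test. On the stated inputs this is over 99.9%. If the source output shows that the difference or the SD was misreported, correct it and recompute.
3. If a margin for a larger SD is given, give it for the Wilcoxon test: at 12 per group and a difference of 60.74, about 90% power up to an SD of 42 and 80% up to 48 to 49, with the simulation assumptions stated.

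The cost is one paragraph in three places, a look at the source output and a short simulation. No patients are added, and neither the design nor the analysis changes.
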